## 10. DATA COLLECTION AND FOLLOW-UP

Registration, baseline assessment, and randomisation should be achieved over 30 minutes. Doctor/nursing attendance with the randomised patient is likely to be required for 1-2 hours post-randomisation to ensure safe and effective thrombolysis, the titration of BP lowering in the active group, and consistent BP recordings. All patients are followed daily for 1 week and then at 28 and 90 days unless death occurs earlier. Investigators will be reimbursed for their time involved in data collection and for local expenses (e.g. printing, internet connection, purchase of medications, copying of brain imaging (CT scans and/or MRIs). Data collection will be kept to a minimum to ensure rapid enrolment and follow-up of patients within the context of routine clinical practice. Key demographic and clinical data will be collected at randomisation. Follow-up data will be collected on 5 occasions: 24 and 72 hours, and 7 (or hospital discharge if sooner), 28 and 90 days. The 28 and 90 day evaluations will be conducted in-person or by telephone, by a trained staff member at the local site who is blind to the treatment allocation. Original records entered directly into database, e.g. data entered directly into database from patient interview or assessment, are acceptable as source data. Brain imaging (CT scan and/or

MRI, with any associated diffusion/perfusion and angiogram images) will be conducted according to standardised techniques at baseline, within 24 hours (ie next day follow-up scan), and at a later stage in all surviving patients who may deteriorate or for other clinical reason during follow-up. Brain imaging (CT scan and/or MRI) must be uploaded to the ENCHANTED server, either directly from the hospital site (if they have suitable broadband internet) or via the RCC office, to be analysed centrally for measurement of any ICH or haemorrhagic complications of the ischaemic lesion, and for future measurement of areas of infarction, ischaemic, penumbra, sites of vessel occlusion. The LCC will keep a hard copy in an uncompressed DICOM format onto a CD-ROM for monitor site verification. Trial management is facilitated by an established internet-based system.

All randomised patients will be followed up to 90 days, or death if prior to 90 days. Patients who do not follow the protocol and/or discontinue allocated management should still be followed up to 90 days as their data will be analysed on the 'intention to treat' principle. **Table 5** illustrates the schedule and nature of the data collection required during the study period. The paper version of the case report forms (CRFs) will be supplied with the procedure manual, as a reference only, together with a guide to completion of each data element and a definition of terms.

All data entry will be completed on a password protected study website. This web-based data management system will allow for real time data query generation for values entered outside of pre-set valid ranges and consistency checking. This system will speed up data reporting and assist overall trial management for all participating centres. In addition to the web-based data entry, BP and drug usage will also be recorded on a paper CRF at the patient's bedside as part of the patient's usual medical record management.

### **10.1 Screening logs**

Each LCC should keep log of all patients presenting to their institution with a diagnosis of acute ischaemic stroke and who were considered for the study but subsequently excluded. The screening log will record patients' initials and date of admission together with a brief description of the main reason as to why a patient was not randomised. The log will be used by the Research Coordinator, PI and the ICC to monitor recruitment and to identify specific barriers to randomisation of eligible patients. It is also a requirement for the reporting of results of clinical trials.

### **10.2 Patient Contact Details log**

Each centre will keep a record of the contact details and information of next-of-kin for all randomised patients. This will be kept at the participating centre in a locked filing cabinet and in accordance with local policies on the custody of confidential clinical trial data. The Patient Contact Details Log will also be used to document any issues arising from the consent procedure, attempts at follow up and information on protocol violations. The Patient Contact Details Log will be used by the Research Coordinator and PI in managing the consent process, follow-up schedule, and in responding to queries from the ICC.

### **10.3 Randomisation assessment**

All patients admitted with AIS will be assessed by the responsible physician for eligibility to the study using a checklist of the eligibility criteria described previously. This form will be kept at the participating site in a locked filing cabinet with the study patient's file.

### **10.4 Baseline Data**

The following information is to be collected on admission:

- Medical history
- Medications at time of admission
- BP, Heart rate (HR), Body weight and scores on the GCS and NIHSS
- Brain imaging findings to confirm the diagnosis of AIS
- Management with neurointervention if performed
- Baseline blood tests
- rtPA details
- Pattern of neurological deficits

All baseline and follow-up brain imaging (CT scans and/or MRI) is to be copied in an uncompressed DICOM format onto a CD-ROM to be uploaded to the ENCHANTED server, either direct from the site or via the RCC. The CD-ROM copy must be kept in the site for monitoring visit (**see Appendix 2**).

## 10.5 Follow up Data

### Day 1 (from randomisation)

The primary goal of assessments within the first 24 hours will be to ensure adherence to the allocated 'rtPA dose' and/or 'BP management' protocol. BP and administered medication will be recorded. BP will be recorded supine in the non-paretic arm from the automated, electronic device used at the Clinical Centre. After the commencement of rtPA, BP will be recorded every 15 minutes for the first hour, then hourly from 1 hour to 6 hours, and 6 hourly from 6 hours to 24 hours. After the commencement of BP lowering treatment, BP will be recorded every 15 minutes for the first hour. When intravenous boluses are given, HR and BP should be re-checked and recorded 5 and 15 minutes later. In addition, the number of systolic BP excursions <140 mmHg, and minimum and maximum systolic BP levels in the first 24 hours, will be recorded. The following information will be recorded.

- BP
- BP lowering medication
- GCS and NIHSS scores at 24 hours
- Follow up brain imaging (CT brain or MRI) should be undertaken within 24 hours after baseline brain imaging and results recorded
- If other imaging investigations are performed (i.e. transcranial doppler), these should be documented in the CRFs
- Follow up blood tests
- Standard stroke care assessment

### Day 3

At day 3, the goal will continue to ensure adherence to the allocated BP management protocol. BP levels will be recorded twice a day after the first 24 hours. The following information will be recorded:

- BP
- GCS and NIHSS scores
- Standard stroke care assessment

### Day 7

On day 7 or on the day of hospital discharge/transfer or death if prior to day 7, the contact details of the patient or caregiver should be confirmed to facilitate follow up assessments. The following information will be recorded:

- BP
- BP lowering medication (medications used during day 2 to day 7)
- Disability assessed with the mRS
- Standard stroke care assessment
- Date of discharge from hospital if this should have occurred at this time

### Day 28 and Day 90

These assessments are to be undertaken by an investigator who was not involved in the clinical management of the patient, and blind to the randomised treatment allocation. On 28±3 days and 90±7 days, all surviving patients will be evaluated through a telephone interview or at a face-to-face consultation. Use of BP lowering agents will be recorded (**see Appendices 1A to 1C**). In addition to the mRS, HRQoL (using the EQ 5D) will be assessed.

### Death

Patients who have died prior to any of the above scheduled assessments, cause of death documentation will be collected with date and time of death. Copies of post-mortem reports, hospital record entry or death certificate, should be kept with the Patient Contact Details log to assist in trial monitoring by the ICC.

### Withdrawal of allocated management and protocol violations

A form will be provided to record the date and circumstances surrounding any deviation from the protocol or missed assessments.

### Consent

Consent will be documented in the patient's progress notes and CRF and the type(s) of consent obtained will also be recorded on the database.

### Serious Adverse Events (SAEs)

All SAEs will be recorded on the SAE form, and completed on the electronic CRF or faxed/emailed from a printed form to the ICC within the prescribed time. Additional information may be requested to provide supplementary information on the event and outcome.

**Table 5 Schedule of evaluations**

Evaluation	Prior to Randomisation	Day				
		1/2	3 a	7 a	28 b	90 b
Eligibility	X					
Brain imaging (CT or MRI ± angiogram)	X	X				
BP	X BP x 2	X ** For time points see the footer	X 12 hourly	X 12 hourly		
Heart rate	X					
Consent (a)	X					

Evaluation	Prior to Randomisation	Day				
		1/2	3 a	7 a	28 b	90 b
Clinical history prior medications	X					
Body weight (kg)	X			X		
Physical exam GCS/NIHSS	X	X	X			
Functional assessment with mRS				X	X	X
HRQoL assessment with EQ 5D					X	X
Routine blood tests	X	X				
BP lowering treatment		X	X	X	X	X
Standard stroke care		X	X	X		
Hospitalised or not				X	X	X
Contact details for Follow-up		X		X		

\*\*

Q 15 min for 1 hour after initiation of rtPA

Q 15 min for 1 hour after initiation of BP lowering

Hourly from 1 hour to 6 hour after initiation of rtPA

6 hourly from 6 hour to 24 hour after initiation of rtPA

At any point where intravenous bolus drugs are administered, BP and HR should be recorded 5 and 15 minutes later.

(a) Or the day of discharge if prior to day 7,

(b) Information collected at a face to face consultation or through a telephone interview

## 11. SERIOUS ADVERSE EVENTS (SAEs)

### 11.1 Definitions

The mechanisms for reporting and notifying SAE are based on the guidelines of the International Conference on Harmonisation Good Clinical Practice (ICH-GCP). As defined by the WHO International Drug Monitoring Centre (1994):

A SAE is any untoward medical occurrence that:

- results in death
- is life threatening in the opinion of the attending clinician (ie the patient was at risk of death at the time of the event; it does not refer to an event that might hypothetically have caused death had it been more severe)
- requires inpatient hospitalisation or prolongation of existing hospitalisation
- results in persistent or significant disability or incapacity

- results in congenital anomaly or birth defect (Note that the females in the study population are likely to be post-menopausal)
- is an important medical event in the opinion of the attending clinician that is not immediately life-threatening and does not result in death or hospitalisation but which may jeopardise the patient or may require intervention to prevent one of the other outcomes listed above

An **unexpected adverse reaction (UAR)** is an adverse reaction that is not consistent with the product information

A **suspected unexpected serious adverse reaction (SUSAR)** is any UAR that at any dose:

- results in death;
- is life threatening (i.e. the subject was at risk of death at the time of the event; it does not refer to an event which hypothetically might have caused death if it were more severe);
- requires hospitalisation or prolongation of existing hospitalisation;
- results in persistent or significant disability or incapacity;
- is a congenital anomaly or birth defect.

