## 11.2 Recording and Reporting

An SAE form must be used to record the details of the event and this will include a full description of the event, classification of the event using the above definitions, the PI's opinion on the causal relationship to the randomised management group and the timing of the event. All SAEs should be reported to the ICC within 24 hours or as soon as the event is recognised. The PI will be required to submit a follow up report to provide further information so that the outcome of the SAE can also be recorded. The PI is responsible for reporting the SAE to the IRB according to local guidelines.

A SUSAR form must be used to record the details of the event and this will include a full description of the event, classification of the event using the above definitions, the PI's opinion on the causal relationship to the suspected medicinal product, and the details of the suspected medicinal product. All SUSARs should be reported to the ICC within 24 hours or as soon as the event is recognised. The PI may be required to provide further details to supplement the initial SAE report and the outcome of the SUSAR will also need to be recorded. The PI is responsible for reporting the SUSAR to the IRB or regulatory administration according to local guidelines and regulatory requirements.

For China sites, apart from the above, all SAEs in relation to use of urapidil (Ebrantil) must also be reported in English by facsimile to Takeda Pharmacovigilance or designee: (i) Fatal and Life Threatening SAEs within 24 hours of the sponsor-investigator's observation or awareness of the event; and (ii) All other serious (non-fatal/non-life threatening) events within 4 calendar days of the sponsor-investigator's observation or awareness of the event.

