### **11.4 Monitoring of SUSARs**

The ICC will closely monitor all SUSARs for any relationship to the study procedures and Protocol or clustering of events at a particular LCC. The ICC will submit all SUSARs to the independent DSMB for review outside of the planned interim analysis meetings. The ICC will also report all SUSARs to the MHRA and in addition will report to local regulatory authorities according to local requirements and guidelines.

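### The SUSAR definition omits one of the six seriousness criteria used for SAEs, so an unexpected reaction that is serious only as an important medical event falls outside the protocol's SUSAR route

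*Protocol*

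**What the plan says.** Section 11.1 of the protocol gives three definitions in sequence.

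- **SAE.** Six criteria. The sixth begins "is an important medical event in the opinion of the attending clinician that is not immediately life-threatening". It sets aside events that cause death or hospitalisation, and covers those "which may jeopardise the patient or may require intervention to prevent one of the other outcomes listed above".
- **Unexpected adverse reaction (UAR).** This "is an adverse reaction that is not consistent with the product information".
- **SUSAR.** This "is any UAR that at any dose" meets one of five listed outcomes. The fifth and last is that it "is a congenital anomaly or birth defect".

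Section 11.2 asks for a form for each type of event. Both forms call for "classification of the event using the above definitions". The SAE form then asks for the investigator's view on causality to the randomised management group. The SUSAR form asks for causality to the suspected product, and for details of that product.

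Section 11.4 sets the regulatory route: "The ICC will also report all SUSARs to the MHRA", with reports to local authorities under local requirements as well. Section 11.3, on SAEs, names the DSMB but no regulator.

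**The concern.** Two lists a few lines apart should agree on what serious means, and they do not. No reason is given for a narrower meaning in the SUSAR definition. The difference decides where a report goes, because the protocol names a regulator only for SUSARs.

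The missing criterion has some bearing on this trial. Patients are already in hospital, so a new admission rarely separates a serious reaction from a non-serious one. An unexpected reaction to an intravenous agent that is treated and reversed at once need not prolong the stay, threaten life or leave disability. It could then be serious only as an important medical event. What is at stake is expedited reporting of that class of reaction, and its labelling as an unexpected reaction to a named product.

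**Working it through.** No arithmetic is involved beyond counting criteria. The check has four steps.

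**1. Compare the two lists in section 11.1.**

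| Criterion | SAE | SUSAR |
|---|---|---|
| Death | yes | yes |
| Life threatening | yes | yes |
| Hospitalisation or its prolongation | yes | yes |
| Persistent or significant disability or incapacity | yes | yes |
| Congenital anomaly or birth defect | yes | yes |
| Important medical event | yes | **no** |
| Total | 6 | 5 |

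The difference is 6 − 5 = 1 criterion.

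**2. Look for wording that restores it.** The UAR definition concerns unexpectedness only, so it adds no seriousness test. The SUSAR definition does not refer back to the SAE list and does not say that the reaction must simply be serious. The published SAP contains no SAE or SUSAR definitions. Nothing restores the criterion.

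**3. Ask whether the list is the working rule.** For the SUSAR form, section 11.2 requires "classification of the event using the above definitions, the PI's opinion on the causal relationship to the suspected medicinal product". The reference is plural and follows both lists, but section 11.1 is the only place where a SUSAR is defined. A site that follows the text applies the five-item list when it decides whether an event is a SUSAR.

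**4. Trace the two routes (sections 11.2 to 11.4, 14 and 17.5).**

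| | SAE only | SUSAR |
|---|---|---|
| To the ICC | within 24 hours or on recognition | within 24 hours or on recognition |
| Causality asked against | randomised management group | suspected product, with its details |
| Investigator reports to | IRB | IRB or regulatory administration |
| Medical Review Committee | yes | reviews it if also filed as an SAE |
| DSMB | yes | yes |
| MHRA and local regulators, from the ICC | not named | yes |
| Manufacturer | urapidil-related SAEs at China sites | no separate SUSAR rule stated |

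A reaction that is suspected, unexpected and serious only by the sixth criterion therefore follows the left-hand column. What it loses is the regulatory route and the form that asks for the suspected product. Someone may still name the drug in the free description of the SAE, but the SAE form as described does not ask for the product or for expectedness.

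**The case against.** The case against giving this much weight is strong on consequence, and most of it stands.

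- **The event is still captured.** It goes on an SAE form to the ICC, the IRB, the Medical Review Committee and the DSMB. Safety data are tabulated in MedDRA terms (section 15.2). Section 11.3 already allows the trial to be amended or stopped through the SAE route. No analysis or stopping rule uses a count of SUSARs. A reader might infer that the recorded harm of intensive lowering is understated. The documents do not support that: the harm is recorded, and the definition is the same in both arms. Control patients may also receive the same intravenous agents (section 6.1.2), although Appendix 1I restricts when acute intravenous therapy is used.
- **The class is narrow.** The SUSAR list keeps the life-threatening criterion and prolongation of an existing stay, which is the part of the hospitalisation criterion that applies to inpatients. Table 4 already lists hypotension, tachycardia, bronchoconstriction and heart block among potential effects of the agents. Many acute reactions may therefore not count as unexpected, though the test is the product information, which is not in the documents.
- **Local rules may be wider.** Sections 11.2 and 11.4 refer to local requirements. A reader might infer that these reactions can never reach a regulator. That is too strong, since a site or the ICC may report more widely in practice. As written, however, this wording governs how an identified SUSAR is reported. It does not widen the definition.
- **Whether regulators require the sixth criterion cannot be shown from these documents.** That is correct. The point rests on the internal mismatch and not on an outside rule.

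The mismatch in the text is not disputed, and neither is the fact that it changes the reporting route.

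**Conclusion.** The inconsistency is real and its consequence is limited. Followed as written, section 11.1 leaves one class of suspected unexpected reaction outside the SUSAR route to the MHRA and local regulators, and off the form that identifies the suspected product. The class consists of reactions that are serious only as important medical events.

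The size cannot be put as a number of events. The documents give no rate for such reactions, so any count would be a guess, and the conclusion does not need one. The class is probably small.

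The conclusion assumes that sites and the ICC apply the printed definitions, and that no separate form or manual outside these documents supplies the missing criterion. Trial harm data, DSMB oversight, endpoints, sample size, alpha and power are not affected. It should be treated as a minor safety-reporting correction.

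**What to change.** In section 11.1, replace the separate five-item list with a cross-reference: a SUSAR is any UAR that meets one or more of the SAE criteria in that section. Adding the sixth criterion to the existing list would have the same effect, but a cross-reference keeps the two definitions from drifting apart again. Change the SUSAR form to match.

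The cost is one line of protocol text, one tick-box on the form and possibly a few more expedited reports. Treatment, data collection for the endpoints and the analysis stay as they are.

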## 11.2 Recording and Reporting

An SAE form must be used to record the details of the event and this will include a full description of the event, classification of the event using the above definitions, the PI's opinion on the causal relationship to the randomised management group and the timing of the event. All SAEs should be reported to the ICC within 24 hours or as soon as the event is recognised. The PI will be required to submit a follow up report to provide further information so that the outcome of the SAE can also be recorded. The PI is responsible for reporting the SAE to the IRB according to local guidelines.

A SUSAR form must be used to record the details of the event and this will include a full description of the event, classification of the event using the above definitions, the PI's opinion on the causal relationship to the suspected medicinal product, and the details of the suspected medicinal product. All SUSARs should be reported to the ICC within 24 hours or as soon as the event is recognised. The PI may be required to provide further details to supplement the initial SAE report and the outcome of the SUSAR will also need to be recorded. The PI is responsible for reporting the SUSAR to the IRB or regulatory administration according to local guidelines and regulatory requirements.

For China sites, apart from the above, all SAEs in relation to use of urapidil (Ebrantil) must also be reported in English by facsimile to Takeda Pharmacovigilance or designee: (i) Fatal and Life Threatening SAEs within 24 hours of the sponsor-investigator's observation or awareness of the event; and (ii) All other serious (non-fatal/non-life threatening) events within 4 calendar days of the sponsor-investigator's observation or awareness of the event.

### **11.3 Monitoring of SAEs**

The ICC will closely monitor all SAEs for any relationship to the study procedures and protocol and clustering of events at a particular site. The protocol will be amended or the study will be stopped earlier if an excess of particular SAEs appear to be protocol related, for example severe hypotensive events requiring emergency treatment in the intensive BP lowering group. In addition, the ICC will submit all SAEs to the independent Data Safety Monitoring Board (DSMB) for review outside of the planned interim analysis meetings.

